2.1.2 Secondary Objectives

Table 3 shows the secondary objectives and endpoints of Part 1 [REDACTED].

Table 3. Secondary Objectives and Endpoints

Part 1 Secondary Objectives	Endpoints

 To characterize the PK profile of BBT-176 after a single oral dose and steady state after multiple doses when given orally alone and in combination with cetuximab 	
 Plasma concentrations of BBT-176 PK parameters ($t_{1/2}$, C_{max}, t_{max}, AUC, C_{trough})

 To evaluate the anti-tumor activity of BBT-176 in selected mutant types by evaluation of the ORR using RECIST version 1.1 	
 ORR per RECIST version 1.1
---	--

Table 4 shows the secondary objectives and endpoints of Part 2 [REDACTED]

Table 4. Secondary Objectives and Endpoints

Part 2 Secondary Objectives	Endpoints

 To evaluate the anti-tumor activity of BBT-176 in selected mutant types by evaluation of the Duration of Response (DoR) and the Progression-Free Survival (PFS) using RECIST version 1.1 	
 DoR per RECIST version 1.1 PFS per RECIST version 1.1

 To evaluate the safety and tolerability of BBT-176 at the PR2D 	
 Incidence of adverse events [AEs] and clinical laboratory abnormalities defined as DLTs

 To characterize the snapshot PK of BBT-176 at steady state after multiple oral doses 	
 Plasma BBT-176 concentrations at steady state PK parameters (C_{max}, t_{max})

2.1.3 Exploratory Objectives

Table 5 shows the exploratory objectives and endpoints of Part 1 (dose-escalation study).

Table 5. Exploratory Objectives and Endpoints

Part 1 Exploratory Objectives	Endpoints

 To investigate the DoR and PFS using RECIST version 1.1 	
 DoR per RECIST version 1.1 PFS per RECIST version 1.1

 To investigate the relationship between the anti-tumor activity and blood-borne biomarkers (i.e., circulating-tumor DNA [ctDNA]) 	
 Pharmacodynamic biomarker (ctDNA)

Table 6 shows the exploratory objectives and endpoints of Part 2 [REDACTED]

Table 6. Exploratory Objectives and Endpoints

Part 2 Exploratory Objectives	Endpoints

 To investigate the relationship between the anti-tumor activity and blood-borne biomarkers (i.e., circulating-tumor DNA [ctDNA]) 	
 Pharmacodynamic biomarker (ctDNA)

2.2 Study Design

2.2.1 Part 1 Study Design: Dose-Escalation Study

○ [REDACTED]
[REDACTED]

[REDACTED]
[REDACTED]
[REDACTED]

2.2.2 Part 1 Study Design: RP2D Exploration study

[REDACTED]
[REDACTED]
[REDACTED]
[REDACTED]
[REDACTED]
[REDACTED]
[REDACTED]
[REDACTED]

2.2.3 Part 2 Study Design: [REDACTED]

[figure not shown]
[REDACTED]
[REDACTED]
[REDACTED]
[REDACTED]
[REDACTED]

[REDACTED]	[REDACTED]	[REDACTED]

[figure not shown]
2.3 Schedule of Activities (SOA)

[REDACTED]
[REDACTED]

[figure not shown]
[REDACTED]							
------------	------------	------------	------------	------------	------------	------------	------------

STATISTICAL ANALYSIS PLAN
BBT176-ONC-001

STATISTICAL ANALYSIS PLAN
BBT176-ONC-001

3. DETERMINATION OF SAMPLE SIZE

3.1 Part 1

Dose-Escalation: up to █ patients with locally advanced or metastatic NSCLS with EGFR mutation are planned for enrollment. █
█
█
█

3.2 Part 2

█
█
█
█
█

█
█
█
█
█

█
█
█
█
█
█
█
█
█
█
█
█
█

█
█
█

4. GENERAL ANALYSIS CONSIDERATION

4.1 Data Summaries

The statistical analyses will be reported using summary tables, figures, and data listings. The International Conference on Harmonization (ICH) numbering convention will be used for all tables, listings, and figures. Unless otherwise specified, all statistical testing will be two-sided and will be performed at the 0.05 significance level. Unless otherwise specified, all confidence intervals (CIs) will be constructed at the 95% confidence level.

The results of the statistical analyses will be reported using summary tables, figures, and data listings. The International Conference on Harmonization (ICH) numbering convention will be used for all tables, listings, and figures. [REDACTED]

[REDACTED] For other estimates, unless otherwise specified, 95% CIs will be provided.

Continuous variables will be summarized with means, standard deviations, medians, minimums, and maximums. Categorical variables will be summarized by counts and by percentages of patients in corresponding categories. Time-to-event variables will be summarized using the Kaplan-Meier estimates. All summary tables will be presented by part and cohort. Baseline summaries will also include a total summary column.

Individual subject data obtained from the electronic case report forms (eCRFs), and any derived data will be presented by subject in data listings. Data from all assessments, whether scheduled or unscheduled, will be included in the listings. Summary tables will be presented for scheduled assessments only.

All analyses and tabulations will be performed using SAS® v9.4 on a SAS server platform. Tables and listings will be presented in rich text format. Upon completion, all SAS programs will be validated by an independent programmer. In addition, all program output will undergo a senior level statistical review. The validation process will be used to confirm that statistically valid methods have been implemented and that all data manipulations and calculations are accurate. Checks will be made to ensure accuracy, consistency with this plan, consistency within tables, and consistency between tables and corresponding data listings. Upon completion of validation and quality review procedures, all documentation will be collected and filed by the project statistician or designee.

4.2 Data Handling

4.2.1 Baseline Value

Unless otherwise specified, the baseline value is defined as the last value obtained before the date and time of the first BBT-176 dose. Post-baseline values are defined as value obtained after the first dose of BBT-176. Change from baseline is defined as a post-baseline value minus the baseline value.

4.2.2 Conventions

Percentages are showed as a rate relative to the total number of subjects with a percent sign (%). For frequency counts of categorical variables, categories whose counts are zero will be displayed for the sake of completeness. For categories with zero counts no percentage will be displayed.

For continuous variables, the precision of the original measurements will be maintained in summaries and listings, when possible. Generally, means, medians and standard deviations will be presented with an increased level of precision; means and medians will be presented to one more decimal place than the raw data, and the standard deviations will be presented to two more decimal places than the raw data.

Summaries of continuous variables that have some values recorded using approximate values (e.g. < or >) will use imputed values. That is, approximate values will be imputed using the closest exact value for that measurement. Listing will present the data in the original format. For tables where rounding is required, rounding will be done to the nearest round-off unit. For example, if the round-off unit is the ones place (i.e., integers), values \geq XX.5 will be rounded up to XX+1 while values < XX.5 will be rounded down to XX.

Listings will present the data in the original format. Durations of AEs and concomitant medications will not be derived using imputed dates but, rather, be set to missing when an event has a partially or completely missing start date or end date.

4.2.3 Standard Calculations

Variables requiring calculation will be derived using the following formula.

- **Study Day** – Study Day 1 is defined as the date of the first treatment. For a given event date, Study Day is calculated relative to the date of first dose of study drug.
$$\text{Study Day} = [\text{Event Date} - \text{First Dose Date}] + 1 \text{ (in days)},$$
where the event date is on or after the first treatment date.
$$= [\text{Event Date} - \text{First Dose Date}] \text{ (in days)},$$
where the event date is before the first treatment date.
- **Duration (Days)** – A duration in days is calculated as the number of days between one date (Date1) and another later date (Date2), including both the start and end days.
$$\text{Duration (days)} = [\text{Date2} - \text{Date1}] + 1 \text{ (in days)}$$
- **Duration (Months)** – A duration in months is calculated as the duration in days divided by 30.4375 (~365.25/12), rounded to one decimal place.
- **Duration (Years)** – A duration in years is calculated as the duration in days divided by 365.25, rounded to one decimal place.
- **Age (Years)** – Age is calculated as the number of years from the date of birth to the date of informed consent using the following formula.
$$\text{Age (years)} = [\text{Date informed consent signed} - \text{Date of birth (in days)}] / 365.25,$$
rounded down to the closest year.

- **Height** – Height entries made in inches (in) are converted to centimeters using the following formula:
$$\text{Height (cm)} = \text{Height (in)} * 2.54$$
, rounded to the one decimal place.
- **Weight** – Weight entries made in pounds (lbs) are converted to kilograms (kgs) using the following formula:
$$\text{Weight (kg)} = \text{Weight (lb)} / 2.2046$$
, rounded to the one decimal place.
- **Body Mass Index (BMI)** – BMI is derived using following formula.
$$\text{BMI (kg/m}^2\text{)} = \text{Weight (kg)} / [(\text{Height (cm)} / 100)^2]$$
, rounded to one decimal place.
- **Temperature** – Temperature entries in degrees Centigrade are converted to degrees Fahrenheit using the following formula:
$$\text{Temperature (degrees Fahrenheit)} = 1.8 * \text{Temperature (degrees Centigrade)} + 32$$
, rounded to one decimal place.

5. ANALYSIS POPULATION

6. STUDY POPULATION

6.1 Patient Disposition

Patient disposition information will be summarized by each dose escalation cohort, overall patients in Part 1 and each expansion cohort, overall patients in Part 2. Summaries will include the number of enrolled patients, the number of patients in each analysis population, and the number of patients completing the study, and the primary reason for discontinuation.

6.2 Demographic and Baseline Characteristics

Demographic variables include: age, sex, ethnicity, and race. Age will be calculated in years relative to the informed consent date. Other baseline characteristics include: medical history, previous cancer treatment, previous tumor tissues collection, weight, height, and BMI.

Descriptive statistics will be presented for medical history, age, weight height, BMI. Frequency counts and percentages will be presented for sex, ethnicity and race. Demographic and baseline characteristics will be summarized by each dose escalation cohort, over all patients in Part 1 and each expansion cohort, overall patients in Part 2. All demographic and baseline characteristics will be presented in a data listing.

6.3 Medical History

The number and percentage of subjects will be summarized by cohort and overall for each body system.

6.4 Prior and Concomitant Medication

Verbatim terms on eCRFs will be mapped to Anatomical Therapeutic Chemical (ATC) class and Generic Drug Names using [REDACTED]

All medications taken within 28 days prior to the administration of study drug and during the course of the study (includes over-the-counter and prescription drugs) and any non-drug treatment/procedures must be recorded on the eCRF, including the reason for treatment, generic name of the drug, dosage, route, and date of administration.

Prior medications are those that start taken prior to the administration of study drug, even if they continue after dosing. Concomitant medications are those that start on or after the date of the first dose of study medication. See Appendix 1 for handling of partial dates for medications; in cases where it is not possible to define a medication as prior or concomitant, the medication will be classified by the worst case—ie, concomitant.

Prior and concomitant medications will be summarized by WHO ATC class include the therapeutic (i.e., the second level of Anatomical Therapeutic Chemical [ATC] classification system code, that is, corresponding to the first 3 figures), preferred name (the fourth level of the ATC code, that is, corresponding to the first 5 figures) and verbatim text and generic drug name for the Safety population. Summaries will be presented by each dose escalation cohort, over all patients in Part 1 and each dose expansion cohort, over all patients in Part 2. The number and percentage of patients using each medication will be presented. Patients may have more than one medication per ATC class and generic drug name. At each level of patient summarization, a patient is counted once if he/she reported one or more medications at that level. Each summary will be ordered in descending order of incidence of ATC class and generic drug name within each ATC class.

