## 7.2 Exclusion Criteria

An individual who meets any of the following criteria will be excluded from participation in this study:

1. Treatment with any of the following:
  - An EGFR TKI, including but not limited to osimertinib, afatinib, dacomitinib, gefitinib, or erlotinib within 8 days of the first dose of study treatment.
  - Small molecule targeted inhibitor other than EGFR inhibitor class, or cytotoxic chemotherapy within 14 days; biologic anticancer medicine (cytokines or antibodies, etc.) within 28 days (before the initiation of BBT-176 treatment) for the systemic treatment of advanced NSCLC
  - Major surgery (excluding placement of vascular access) within 4 weeks of the first dose of study treatment
  - Radiotherapy with a limited field of radiation for palliation within 1 week of the first dose of study treatment
  - Patients receiving radiation to more than 30% of the bone marrow or with a wide field of radiation within 6 weeks of the first dose of study treatment
  - Patients receiving CYP2C8 or P-gp strong inhibitor (see Appendix 4)
2. Any unresolved toxicities from prior therapy greater than NCI Common Terminology Criteria for Adverse Events (CTCAE v5.0) Grade 1 at the time of starting study treatment, with the exception of alopecia and Grade 2 neuropathy related to prior platinum-therapy
3. Spinal cord compression or brain metastases, unless asymptomatic and stable fulfilling one of following:
  - Not requiring active treatments prior to start of study treatment
  - Requiring stable dosing regimens of low-dose oral corticosteroid (up to 20 mg prednisone/day or equivalent) for at least 4 weeks prior to the first dose of study treatment
4. Even if the patient has progressed after EGFR TKI therapy, if there is a treatment proven to be effective, the patient should receive the treatment first. This includes cases where documented evidence of *MET* amplification, *HER2* mutation, or SCLC transformation exists and treatments or clinical trials that have been proven for the corresponding mutations are available.
5. Any evidence of severe or uncontrolled systemic diseases, including uncontrolled hypertension and active bleeding diatheses that in the Investigator's opinion makes it

[figure not shown]

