### **8.5 Prior and Concomitant Therapy**

Prior medication will be recorded as part of the past medical history.

Concomitant therapy is defined as any medicinal product, prescribed or over-the-counter, taken by a patient other than the study drug. Use of concomitant medications will be recorded and reported. The Investigator will have discretion to prescribe medications which are recommended by public treatment guidelines to prevent or mitigate adverse events in cancer patients, e.g., nausea, vomiting, or diarrhea.

The Investigator will be responsible for preventive vaccination of the subjects according to the available public health policy of the jurisdiction where this clinical trial is being conducted. The Investigator may discuss with the Sponsor on individual decisions.

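### SAP 6.4 sorts medications by start date alone, so a drug already in use at first dose and continued during BBT-176 treatment is labelled prior only, contrary to protocol 8.5

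*SAP*

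**What the plan says.** SAP 6.4 gives two definitions, both based on the start date. For earlier starts: "Prior medications are those that start taken prior to the administration of study drug, even if they continue after dosing". For later starts: "Concomitant medications are those that start on or after the date of the first dose of study medication". Where the dates do not settle the matter, "the medication will be classified by the worst case", meaning concomitant, and Appendix 1 is cited for partial dates. On reporting, "Prior and concomitant medications will be summarized by WHO ATC class" and by generic drug name in the Safety population, with counts and percentages of patients by cohort. A patient counts once at each level. The section does not say whether prior and concomitant drugs go in separate tables.

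Protocol 8.5 puts it differently: "Concomitant therapy is defined as any medicinal product, prescribed or over-the-counter, taken by a patient other than the study drug". It adds that "Use of concomitant medications will be recorded and reported" and that "Prior medication will be recorded as part of the past medical history". It gives no cut-off date between the two categories.

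**The concern.** A concomitant-medication summary should show what patients were taking while exposed to study drug, so that adverse events, laboratory changes and ECG findings can be read against it. The SAP rule instead shows what patients newly started while exposed. Long-term treatment that runs through the study is labelled with drugs that ended before the first capsule.

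The protocol itself creates a group in this position. Exclusion criterion 3 lets in patients with asymptomatic, stable brain metastases or cord compression who are on low-dose oral steroid: "Requiring stable dosing regimens of low-dose oral corticosteroid", held for at least 4 weeks before first dose. If the steroid continues on study, it is an on-treatment drug that the SAP calls prior.

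The SAP's fallback also points the other way. A drug whose timing is unknown is treated as concomitant for caution, while a drug known to be taken on treatment is not.

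**Working it through.** The point concerns a classification rule. The plan states no figure to reproduce, and no script was run. The check applies each document's wording to the possible timings.

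| Timing of the medication | SAP 6.4 | Protocol 8.5 | Agreement |
|---|---|---|---|
| (a) Started and stopped before first dose | Prior | Can be read as prior | Yes |
| (b) Started before first dose, continued after it | Prior only | Concomitant | **No** |
| (c) Started on or after the first-dose date | Concomitant | Concomitant | Yes |
| (d) Status not determinable from the dates | Concomitant (worst case) | No rule given | No conflict |

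The disagreement is confined to row (b). It is not a matter of loose drafting, because the SAP's definition of prior expressly covers drugs that continue after dosing. A drug started on Day 1 before the dose satisfies both SAP definitions, a small overlap that the section does not resolve.

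A second place in the protocol supports the wider meaning. Exclusion criterion 6 lists concomitant medication known to prolong QT among the reasons not to enrol. At screening that can only mean a drug already being taken.

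The effect on the reported counts follows from the rule that each patient counts once. For one drug or ATC class in one cohort, let A, B and C be the sets of patients with use of type (a), (b) and (c), with known dates.

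- Patients exposed on treatment: |B ∪ C|.
- Concomitant count under SAP 6.4: |C|. The shortfall is |B ∪ C| − |C| = |B \ C|, the patients whose only on-treatment use was already ongoing at first dose.
- Prior count under SAP 6.4: |A ∪ B|, which mixes stopped and continuing drugs.
- If both labels are pooled in one table: |A ∪ B ∪ C|. This exceeds the on-treatment count by |A \ (B ∪ C)|, the patients who had only stopped before first dose. The eCRF covers the 28 days before study drug, so such patients can exist.

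The labelled count is therefore too low whenever B \ C is not empty, and the pooled count is too high whenever A \ (B ∪ C) is not empty. Neither layout isolates exposure during treatment. The documents give no medication frequencies, so the shortfall for a drug can lie anywhere from zero to the whole cohort.

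For the steroid example, at least 4 weeks is at least 4 × 7 = 28 days before first dose. The start date therefore always precedes study drug, and a continuing course is always row (b).

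**The case against.** The strongest reply is that nothing disappears. SAP 6.4 requires medications from the 28 days before study drug and throughout the study to be recorded. It summarises prior and concomitant drugs in the same sentence, and SAP 4.1 puts individual data in listings. A reader might infer that every ongoing drug drops out of the report. The documents do not support that: these drugs appear under another label, and no separate concomitant table is promised from which they could be missing. This stands as to loss of data. It does not rescue the label, because a pooled table still cannot show what was taken on treatment.

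A reader might also infer that a patient admitted on stable steroid can never be counted as a concomitant steroid user. That is too strong. A new steroid started on study would count, and so would one whose dates cannot be resolved.

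Nor can QT-active and interacting drugs carry the argument. Exclusion criterion 6 bars QT-prolonging medication at entry and exclusion criterion 1 bars strong CYP2C8 or P-gp inhibitors. If begun on study, such drugs are concomitant under the SAP as well. Other interacting drugs may remain, but several restrictions in protocol 8.5.2 are redacted and the number cannot be judged.

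Two further replies have partial force. Protocol 8.5 gives no time window, so it does not itself draw the line between prior and concomitant. Even so, its definition contains no start-date condition, and a drug taken during treatment falls within it. The worst-case sentence is a fallback for indeterminate dates and not a rival definition, so the contrast with it is an oddity and not a contradiction.

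**Conclusion.** The point holds as a misclassification. Under SAP 6.4 as written, a drug with known dates that started before first dose and continued on BBT-176 is prior only, which conflicts with protocol 8.5 and with the wording of exclusion criterion 6. Concomitant use is understated and the prior category is mixed.

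The size is minor to moderate. The summary is descriptive, in an open-label trial without randomisation. None of the visible ORR, DoR, PFS, adverse-event, laboratory or ECG methods uses a concomitant-medication flag, and no visible dose decision rests on it. A reader might infer that efficacy results or dose selection are affected; the documents give no support for that.

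The conclusion rests on three assumptions. First, the content of SAP Appendix 1 is not shown; it is taken to govern partial dates only, as SAP 6.4 describes it. Second, the protocol version on which the SAP is based is redacted. The SAP objectives still mention cetuximab combination, which the current protocol objectives do not, so protocol 8.5 may have read differently in that version. The conflict is with the current protocol. Third, a continuing drug is taken to be one eCRF record that keeps its original start date.

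**What to change.** In SAP 6.4, replace the two definitions along these lines:

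- *Prior:* last taken before the date of first dose of BBT-176.
- *Concomitant:* taken at any time on or after the date of first dose, whatever the start date. Drugs started earlier and continuing are concomitant and may be flagged as ongoing at baseline.

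Keep the worst-case rule for medications whose status cannot be determined, and extend it explicitly to a missing stop date. State that prior and concomitant medications are tabulated separately. Using the date, not the time, of first dose also settles the Day 1 overlap. A matching sentence in protocol 8.5 giving the cut-off would be useful at the next amendment but is not essential.

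The cost is a few lines of SAP text and one changed derivation. No new data should be needed: SAP 6.4 already calls for administration dates, and SAP 4.2.2 already refers to start and end dates for concomitant medications.
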